#### 7.5. Missing data

The aim is to minimize the missing data to a minimum. If some important data cannot be collected, we will consider using multiple imputation. The method will be multiple imputation with chained equations (mice)

## 7.6. Exploratory analysis and sensitivity analysis

No exploratory or sensitivity analyses are planned due to the limited sample size.

### 7.7. Reporting deviations

If deviations from the statistical analysis plan occur, we will present and explain these changes in the methods section of the paper.

## 7.8. Handling of imbalance of subjects per site

As the pilot study sites are in the same area, we will consider them to be one study site.

Version No: 1.1

Date: 2024-10-27 32 (48)

# 8. Data management and protection

Subjects who participate in the clinical investigation are coded with a specific clinical investigation identification number. All subjects are registered in a subject identification list (subject enrolment and identification list) that connects the subject's name and personal number with a clinical investigation identification number.

All data will be registered, managed, and stored in a manner that enables correct reporting, interpretation, and verification.

## 8.1. Data collection and Case Report Forms

Follow up and data collection will be performed in three different and separate levels/occasions.

#### A. For all patients after finished resuscitation:

- Prehospital Digital CRF 1 (see below)
- Swedish Register of Cardiopulmonary Resuscitation (SRCR) part 1, pre-hospital treatment, patient characteristics and short-term outcome
- ECG files from corpuls3 used by including ambulance unit
- Ambulance charts
- EMS emergency dispatch organization time delays (from the Swedish emergency dispatch organization SOS-Alarm)

#### B. For all patients surviving to hospital admission:

- The SRCR part 2, in-hospital treatment survival to discharge and date of discharge
- For patients undergoing angiography, variables from the Swedish Coronary Angiography and angioplasty register (SCAAR)
- Medical charts, length of stay at ICU, length of stay in hospital and ICD-codes at discharge

## C. All patients surviving to 30, 90 and 180 days:

- Neurological function (mRS, CPC) at 30 days
- Neurological function (mRS, CPC), self-reported cognitive function (Single item) and Health-related quality of life (EQ-5D-5L, EQ VAS, PHQ-9, GAD, LiSAT-11, MFIS-21) at 90 days
- Neurological function (mRS, CPC), self-reported cognitive function (Single item) and Health-related quality of life (EQ-5D-5L, EQ VAS, PHQ-9, GAD, LiSAT-11, MFIS-21) at 180 days

#### 8.1 Prehospital CRF1, Characteristics during the resuscitation phase

After completing the care of the patient, the study responsible EMS-unit will report a digital prehospital CRF. This is practically done by using and reading a study specific QR-code located on the back of the specific randomization envelope / sheet using a smart-phone. This will open a webpage automatic registration of time of registration and information to be filled in when opened.

Version No: 1.1

Date: 2024-10-27 33 (48)

The prehospital CRF will contain basic on-site information such as which ambulance that performed randomization, randomization study number, time and date of cardiac arrest, number of shocks prior to EMS arrival and number of shocks prior to randomization, treatment allocation, electrode placement for each defibrillation, number of defibrillations before DSD, ROSC and if the patients survived the event. Furthermore, if the patient has a known identity, personal id-number will be included to enable follow up. If the patients do not have a known identity a temporary identification number will be used.

The prehospital CRF allows for real-time monitoring of randomization and allows for early start of follow-up.

Other core resuscitation characteristics will later be reported and collected from the SRCR part 1 and ambulance charts. This registry data is standard and mandatory for all EMS personal to report and contains resuscitation and patient characteristics and reporting to the register is part of routine documentation.

ECG files from defibrillators. All data stored in the defibrillators after each use in the trial will be exported to a secure server and analyzed for defibrillation safety and CPR quality.

#### 8.2 In hospital CRF (See supplemental NN) in hospital treatment

In-hospital CRF will cover core in-hospital treatment. The in hospital CRF will collect core data from the mandatory SRCR part 2 such as length of stay and survival to hospital discharge.

Please see supplemental file intrahospital CRF.

For patients that undergo coronary angiography, core variables regarding coronary anatomy, number of vessels with significant atherosclerotic stenosis and coronary intervention will be collected from the Swedish Coronary Angiography and angioplasty register (SCAAR)

#### 8.3 Neurological and patient reported Follow up CRF, 30, 90 and 180 days

For patients who survive to hospital discharge and have signed an informed consent to further participation in the trial a specific follow-up team separated and blinded from the care and randomized allocation (intervention or control) will be responsible for neurological follow-up. Neurological function will be assessed according to the modified Ranking Scale (mRS) and the Cerebral Performance Category (CPC) scale at 30, 90 and 180 days. The mRS scale includes categories 1-6, where higher numbers indicate more severe

0 = no symptoms,

disability.

- 1 = no significant disability—able to carry out all usual activities, despite some symptoms,
- 2 = slight disability—able to look after own affairs without assistance but unable to carry out all previous activities,
- 3 = moderate disability—requires some help but able to walk unassisted,
- 4 = moderately severe disability—unable to attend to own bodily needs without assistance and/or unable to walk unassisted,
- 5 = severe disability—requires constant nursing care and attention, bedridden, incontinent,

Version No: 1.1

Date: 2024-10-27 34 (48)

and 6 = dead.

The CPC scale includes categories 1-5, where higher numbers indicate more severe neurological impairment;

- 1 = Conscious, alert, able to work and lead a normal life. May have minor psychologic or neurologic deficits (mild dysphasia, non-incapacitating hemiparesis, or minor cranial nerve abnormalities),
- 2 = Conscious. Sufficient cerebral function for part-time work in sheltered environment or independent activities of daily life (dress, travel by public transportation, food preparation). May have hemiplegia, seizures, ataxia, dysarthria, or permanent memory or mental changes, 3 = Conscious. Dependent on others for daily support (in an institution or at home with exceptional family effort). Has at least limited cognition. This category includes a wide range of cerebral abnormalities, from patients who are ambulatory but have severe memory disturbances or dementia precluding independent existence, to those who are paralyzed and
- 4 = Unconscious. Unaware of surroundings, no cognition. No verbal and/or psychologic interaction with environment, and
- 5 = Brain dead, circulation preserved. Death at discharge.

can communicate only with their eyes, as in the "locked in" syndrome,

Patients that are alive at 90 and 180 days will also be evaluated for cognitive function and health-related quality of life using the following self-reporting measures:

The single item for self-reported cognitive function is developed and used by the SRCR. It is formulated "How do you perceive your memory-, concentration- and/or planning ability today compared to before your cardiac arrest?". The responses are rated on a five-point scale from "It is much better" to "It is much worse".

The EuroQol 5D 5L (EQ-5D-5L) consists of 5 health domains (mobility, self-care, usual activities, pain/discomfort, and anxiety/depression. Each dimension is rated on a five-point scale, ranging from 1 "no problems" to 5 "extreme problems".

The EQ VAS is a single item measure evaluating "your health today", using a visual analogue scale from 0 ("worst possible health") to 100 ("best possible health").

The 11-item Life Satisfaction questionnaire (LiSat-11) consists of 11 single items, one representing overall satisfaction with life (life as a whole) and 10 addressing specific domains of life satisfaction (vocation, economy, leisure, friends, sexual-life, self-care, family-life, partner relation, physical health, and psychological health). Each domain is assessed on a six-point scale ranging from "Very dissatisfied" to "Very satisfied".

The Patient Health Questionnaire (PHQ-9) is a screening measure for symptoms of depression. It consists of 9 (+1) items with responses rated on a four-point scale from 0 "not at all" to 3 "nearly every day". The item scores are summarized to a total score from 0-27, with higher scores indicating a more probable presence of depression. The last question addresses the possible impact on daily activities.

Generalized Anxiety Disorder 7-item scale (GAD-7) is a screening measure for symptoms of anxiety. It consists of 7 (+1) items with responses rated on a four-point scale from 0 "not at all" to 3 "nearly every day". The item scores are summarized to a total score from 0-21, with higher scores indicating a more probable presence of anxiety. The last question addresses the possible impact on daily activities.

Version No: 1.1

Date: 2024-10-27 35 (48)

The Modified Fatigue Impact Scale (MFIS) is a measure of how fatigue impacts life related to the respondents physical, cognitive, and psychosocial functioning. The original scale consists of 21 items. Responses are rated on a five-point scale from "never" (0) to "almost always" (4), resulting in a total score (0-84) and three subscale scores. Higher scores indicate a greater impact of fatigue on a person's activities.

Variables from the neurological follow-up will be entered directly to a secure REDCap database at KI.

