#### 6.2.3. Tertiary endpoints

- Survival to hospital admission
- Survival to hospital discharge
- Survival at 30 days
- Neurological function (mRS and CPC) at 30 days
- Neurological function (mRS and CPC) and Health-related Quality of life at 90 days
- Neurological function (mRS and CPC) and Health-related Quality of life at 180 days

Version No: 1.1

Date: 2024-10-27 26 (48)

The tertiary outcomes were chosen to comply with the "Core Outcome Set for Cardiac Arrest in Adults" advisory statement From the International Liaison Committee on Resuscitation.[13]

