## 7. Statistical considerations.

## 7.1. Analysis population

The principal analysis strategy will be on an "intention to treat" basis. All randomized patients will be included in this analysis.

Further analysis will be performed after exclusion of patients with post randomization exclusion criteria (such as not in cardiac arrest, not VT/VF or exclusion criteria that were not evident at the time of randomization) in a modified intention to treat (mITT) analysis.

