## 13.2 Consent process

The chance of surviving cardiac arrest is very low, overall 90% of the patients die. In the OHCA sub-set of patients with VT/VF survival at 30 days is about 30%. In a cardiac arrest scenario treatment of CPR and defibrillation must be started immediately in order to increase the chance of survival.

Due to the nature of the condition of sudden cardiac arrest, informed consent for participating in the study cannot be obtained from the subject at the scene since the victim is unconscious at the time for study inclusion and the EMS personnel or the sponsor has no previous information about the patients willing to participate in the study or not. According to the EU:s Clinical Trials Regulation clinical course in patients that regains circulation after a in hospital cardiac arrest shows a wide variety, from irreversible to reversible circulatory shock, irreversible brain damage and death to neurological intact survival and fast recovery in cognitive functions. Therefore, the strategy for obtaining informed consent varies dependent on patient outcome.

The strategy for obtaining informed consent is as follows according to the patient's status

- 1. The patient who is not regaining circulation and is declared dead at the scene of the arrest. No consent will be obtained
- 2. The patient who survives the initial resuscitation phase, is transferred to hospital and is conscious. Information about the study (both oral and written) will be given during hospital stay. The information includes the purpose of the study, the study intervention, possible risks and benefits from participating in the study and who is legal responsible for the study. In the information it is also clarified that all

Version No: 1.1

Date: 2024-10-27 39 (48)

- participation is voluntary, the right to not participate in the study and the right to withdraw participation. The informed consent is obtained.

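### Section 8.3 limits neurological follow-up to discharged, consented patients while 8.1 C covers everyone alive at each visit, so patients still in hospital at day 30 could go unscored

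*Protocol*

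**What the plan says.** Section 6.2.3 lists "Neurological function (mRS and CPC) at 30 days" as a tertiary endpoint, with further assessments at 90 and 180 days, and attaches no condition about discharge or consent. "Survival at 30 days" is listed separately.

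Section 8.1 C sets out late data collection for "All patients surviving to 30, 90 and 180 days".

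The neurological follow-up CRF section, numbered 8.3 (a number also used for archiving), assigns a blinded team to follow-up "For patients who survive to hospital discharge and have signed an informed consent to further participation in the trial". It continues: "Neurological function will be assessed according to the modified Ranking Scale (mRS) and the Cerebral Performance Category (CPC) scale at 30, 90 and 180 days". Both scales it prints have a category that includes death: 6 on the mRS, and for the CPC "5 = Brain dead, circulation preserved. Death at discharge". Further down, the same section defines the cognitive and quality-of-life set simply as patients alive at 90 and 180 days.

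Section 6.5 describes blinded collection at 30, 90 and 180 days and mentions no discharge limit. Section 7.1 says of the intention-to-treat analysis: "All randomized patients will be included in this analysis". Section 13.2 provides for consent by a legally designated representative when the patient cannot consent or cannot sign.

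**The concern.** Sites and the follow-up team cannot follow both 8.1 C and 8.3. A patient alive at day 30 but not yet discharged belongs to the first set and not to the second. If that patient goes home later, the day-30 assessment has already been missed. If the patient dies in hospital after day 30, the 8.3 condition is never met, although the patient was alive at the visit.

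This concerns what is collected, not how it is analysed, so a statistical analysis plan cannot repair it afterwards. The omission is unlikely to be random: patients in hospital a month after a cardiac arrest are probably worse neurologically than those already home. Section 13.2 also shows that consent comes latest for patients with reduced consciousness, dementia or aphasia, and 8.3 does not say that a representative's signature satisfies its consent condition.

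The pilot is meant to inform the main study (5.2.2 and 7.4). A collection rule carried over unchanged would take the gap with it.

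**Working it through.** No figure in the protocol is contested, and 7.4 states that no sample size calculation is made. The check is a comparison of texts, followed by a rough scale.

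**Who is assessed, by type of patient at day 30**

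- Alive, discharged, consent signed: in 8.1 C and in 8.3.
- Alive, still in hospital: in 8.1 C, not in 8.3.
- Alive, consent given only by a representative: in 8.1 C; unclear in 8.3, which can be read as asking for the patient's own signature.
- Dead: in neither set, because no visit is possible. Section 13.2 says of one such group: "The patient who is not regaining circulation and is declared dead at the scene of the arrest. No consent will be obtained".

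The conflict between the two sections therefore concerns living patients only. It falls mainly at day 30, on the assumption that few patients are still in hospital at 90 or 180 days.

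**Scale**

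Inputs: 40 patients, 30 DSD and 10 standard (6.3.3); 30-day survival in VT/VF of about one-third (4.6) or about 30% (13.2). These survival figures are for VT/VF arrests in general; applying them to this population and to both arms is an assumption.

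Expected alive at day 30 = n × survival:

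- At 30%: 40 × 0.30 = 12 (30 × 0.30 = 9 DSD, 10 × 0.30 = 3 standard); deaths 40 − 12 = 28.
- At one-third: 40/3 = 13.3 (10 DSD, 3.3 standard); deaths 26.7.

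Let m be the number alive but in hospital at day 30. The documents give no length of stay, so m is an assumption, shown over a range:

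- m = 0: no loss.
- m = 1: 1/12 = 8.3% or 1/13.3 = 7.5% of the living; 1/40 = 2.5% of those randomised.
- m = 2: 16.7% or 15.0% of the living; 5.0% of those randomised.
- m = 3: 25.0% or 22.5% of the living; 7.5% of those randomised.

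If known deaths are scored, the number with a day-30 mRS is 28 + (12 − m) = 40 − m at 30% survival. The share missing over all randomised patients is then m/40. With about 3 living patients expected in the standard arm, one missed there would be about a third of that arm's assessable survivors.

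**The case against.** The best defence is that the 8.3 sentence only allocates work to a follow-up team and was not meant to narrow the endpoint. Sections 6.2.3, 6.5 and 8.1 C carry no discharge limit, and the representative route in 13.2 means that severe impairment does not by itself exclude anyone. The number affected could be zero. Losing inpatients from both arms would raise the apparent level of function, but it would bias the comparison only if the loss differed by arm, and nothing in the protocol shows that it would. All of this limits the size of the point. It does not remove the mismatch, because staff working from 8.3 would still have grounds not to assess an inpatient at day 30. The consent condition itself is legitimate; only its wording needs to admit the representative.

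A reader might go further and infer that deaths are dropped from the mRS and CPC comparison and that intention to treat is broken. The documents do not support that. Sections 8.1 C and 8.3 govern who is assessed, and 7.1 keeps all randomised patients in the analysis. Vital status is collected apart from this visit (CRF1, the resuscitation registry and the 30-day survival endpoint), and both scales list death, which fits scoring deaths at least as well as omitting them. A survivor-only comparison would indeed be thin: about 9 v 3 or 10 v 3 patients. The chance of at most one control survivor, (1 − s)^10 + 10s(1 − s)^9, is 14.9% at s = 0.30 and 10.4% at s = 1/3. Those figures describe an analysis that the protocol never specifies, so they do not measure this point.

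**Conclusion.** The point holds as a contradiction about which living patients are assessed. Under 8.3 as written, patients alive but still in hospital would have no mRS or CPC at day 30, and their data would probably be missing not at random. The size cannot be fixed from the protocol: about 8% of expected day-30 survivors for each patient missed, with the number missed unknown and possibly nil. This rests on survival of 30% to one-third and on the judgement that inpatients at day 30 are more impaired than those discharged.

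Severity is minor. The endpoints are tertiary, the trial is a 40-patient feasibility pilot without hypothesis testing, and no primary feasibility or safety target is touched. How deaths enter the scales needs only a clarification and is not an error.

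**What to change.** Reword the opening of the neurological follow-up section (8.3) to match 8.1 C:

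- Every patient alive at each of the three visits is assessed, whether discharged or in hospital, with consent from the patient or, under 13.2, from the legally designated representative.
- The blinded team does the scoring, with allocation masked in any chart material it uses.
- Patients alive but not assessed are reported by arm, with reasons.
- As a clarification consistent with 7.1 and the printed categories, deaths known by a visit count as mRS 6 and CPC 5. This helps because the CPC label ties death to discharge, whereas the endpoint is set at fixed days.

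While the paragraph is open, correct the stated mRS range, which is given as 1 to 6 although the list runs from 0 to 6.

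The cost is a few lines of text and a small number of in-hospital or chart-based scores. The downside is that such scores are coarser than those from a follow-up visit, and that charts can reveal allocation, so the masking has to be done with care to preserve the blinding promised in 6.4 and 6.5.

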## 8.2. Data cleaning and database lock

All data reported from prehospital CRF, in-hospital CRF and neurological follow up CRF will be digitally entered to a study specific data base (red-Cap). The database will be stored at a secure server at the Karolinska Institute.

All essential documentation and trial records will be stored at in conformance with the applicable regulatory requirements. Access to stored information will be restricted to authorized personnel. Data will be stored in a secure area with access restricted to staff working on the trial. Any data that are transferred out of the secure environment (for example for statistical analysis) will adhere to standard procedures for secure data management. All personal data will be handled according to the standard procedures for the current registries and medical records and in accordance with the General Data Protection Regulation (GDPR). In the study database all personal data will be pseudonymized and only handled on group level. Personal numbers and all other data that can lead to identification of subjects included in the study will be coded and keys for decoding will only be accessible to key persons in the project. The database will also only be accessible to key persons in the project.

## 8.3. Archiving

The PI and sponsor will maintain the essential clinical investigation documents in the investigation site files archive and sponsor files archive, respectively. The sponsor shall keep all documentation and data for at least 10 years after the clinical investigation has ended. The PI will archive all local investigation documentation for at least 10 years or as long as stipulated by the local institution.

## 8.4. Data protection

If any part of the data is handled by any other organization, inside or outside the European Union, appropriate agreements and/or other documentation will be established, to ensure that the data processing is performed in accordance with the provisions of the General Data Protection Regulation (EU ordinance 2016/679, GDPR) and other relevant legislation, before any data transfer takes place.

Version No: 1.1

Date: 2024-10-27 36 (48)

The content of the informed consent form shall comply with relevant integrity and data protection legislation. In the subject information and the informed consent form, the subject will be given complete information about how collection, use and publication of their clinical investigation data will take place. The subject information and the informed consent form will explain how clinical investigation data are stored to maintain confidentiality in accordance with national data legislation.

The informed consent form will also explain that for verification of the data, authorized representatives of the sponsor, as well as relevant authority, may require access to parts of medical records or study records that are relevant to the clinical investigation, including the subject's medical history.

